12.1 Extent of Exposure

The mean number of days from first to last dose was 179.8 days in the udenafil group and 182.7 days in the placebo group ([Table 23](#)). Mean percent compliance with study drug was 89.92% in the udenafil group and 89.97% in the placebo group. Compliance results are listed by subject in [Listing 16.2.5.1](#).

Table 23: Extent of Exposure and Compliance with Study Drug (Safety Population)

	Udenafil (N=200)	Placebo (N=200)	Total (N=400)
Number of days from first to last dose	(N=200)	(N=200)	(N=400)
Mean (SD)	179.8 (32.23)	182.7 (26.78)	181.3 (29.63)
Median	183.0	183.0	183.0
Minimum, maximum	5, 344	8, 280	5, 344
Percent compliance (%)	(N=174)	(N=185)	(N=359)
Mean (SD)	89.92 (10.283)	89.97 (10.342)	89.94 (10.299)
Median	92.89	93.20	93.09
Minimum, maximum	48.5, 100.0	39.6, 100.0	39.6, 100.0

SD=standard deviation

Source: [Table 14.3.1.1](#)Program: [t_14_3_1_1.sas](#)

The mean (standard deviation) udenafil concentration was 174.99 (112.00) ng/mL at 2 hours \pm 30 minutes after dosing on Day 1 and 259.19 (166.062) at Week 26 ([Table 14.3.1.2](#)). A summary of log-transformed udenafil concentrations is provided in [Table 14.3.1.3](#). The mean (standard deviation) concentration of the DA-8164 metabolite was 74.34 (65.471) ng/mL at 2 hours \pm 30 minutes after dosing on Day 1 and 225.59 (161.602) at Week 26 ([Table 14.3.1.4](#)). A summary of log-transformed DA-8164 concentrations is provided in [Table 14.3.1.5](#). Concentrations of udenafil and DA-8164 are listed by subject and study visit in [Listing 16.2.5.2](#).

12.2 Adverse Events (AEs)

12.2.1 Brief Summary of Adverse Events

A notably larger percentage (≥ 5 percentage points) of udenafil-treated than placebo-treated subjects reported at least 1 TEAE (79.0% versus 67.5%) and drug-related TEAE (66.0% versus 42.5%). The incidence of TEAEs of Grade ≥ 3 , serious TEAEs, drug-related serious TEAEs, and TEAEs resulting in temporary discontinuation (identified as drug interrupted in listings) or permanent discontinuation of study drug was similar between treatment groups ([Table 24](#)).

Table 24: Overall Summary of Treatment-emergent Adverse Events (Safety Population)

Subjects with ≥ 1 :	Udenafil (N=200) n (%)	Placebo (N=200) n (%)
TEAE	158 (79.0)	135 (67.5)
Drug-related TEAE	132 (66.0)	85 (42.5)
TEAEs of Grade ≥ 3	10 (5.0)	6 (3.0)
Serious TEAEs	14 (7.0)	10 (5.0)
Drug-related serious TEAEs	4 (2.0)	2 (1.0)
TEAE that led to temporary or permanent discontinuation of study drug	18 (9.0)	13 (6.5)

TEAE=treatment-emergent adverse event

Source: [Table 14.3.2](#)Program: [t_14_3_2.sas](#)

12.2.2 Display of Adverse Events

TEAEs reported by $\geq 5\%$ of subjects in the udenafil group ([Table 14.3.5](#)) included headache (39.0%), flushing (14.5%), epistaxis (10.0%), nasopharyngitis (10.0%), nausea (9.5%), dizziness (8.5%), vomiting (7.5%), upper respiratory tract infection (7.0%), erection increased (6.3% of males), spontaneous penile erection (6.3% of males), influenza (5.5%), chest pain (5.0%), pharyngitis streptococcal (5.0%), and rash (5.0%). TEAEs reported by $\geq 5\%$ of subjects in the placebo group included headache (25.5%), chest pain (9.0%), dizziness (9.0%), upper respiratory tract infection (8.5%), nasopharyngitis (6.5%), flushing (6.0%), and fatigue (5.5%).

A notably greater percentage (≥ 5 percentage points) of subjects in the udenafil group as compared to the placebo group reported headache (39.0% versus 25.5%), flushing (14.5% versus 6.0%), epistaxis (10.0% versus 3.0%), nausea (9.5% versus 4.5%), and erection increased (6.3% of males versus 0.8% of males) ([Table 14.3.5](#)).

Common TEAEs (reported by $\geq 5\%$ of all subjects) are summarized in [Table 25](#).

Table 25: Most Common (≥5% of All Subjects) Treatment-emergent Adverse Events (Safety Population)

System Organ Class Preferred Term:	Udenafil (N=200) n (%)	Placebo (N=200) n (%)
Subjects with ≥1 TEAE	158 (79.0)	135 (67.5)
Gastrointestinal disorders	55 (27.5)	33 (16.5)
Nausea	19 (9.5)	9 (4.5)
Vomiting	15 (7.5)	6 (3.0)
General disorders and administration site conditions	33 (16.5)	39 (19.5)
Chest pain	10 (5.0)	18 (9.0)
Infections and infestations	69 (34.5)	60 (30.0)
Nasopharyngitis	20 (10.0)	13 (6.5)
Upper respiratory tract infection	14 (7.0)	17 (8.5)
Nervous system disorders	95 (47.5)	65 (32.5)
Dizziness	17 (8.5)	18 (9.0)
Headache	78 (39.0)	51 (25.5)
Respiratory, thoracic and mediastinal disorders	45 (22.5)	29 (14.5)
Epistaxis	20 (10.0)	6 (3.0)
Vascular disorders	32 (16.0)	14 (7.0)
Flushing	29 (14.5)	12 (6.0)

TEAE=treatment-emergent adverse event

Source: [Table 14.3.3](#) and [Table 14.3.5](#)Program: [14_3_ae_tables.sas](#)

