9.3.1 Inclusion Criteria

Only subjects who met all of the following criteria were included:

1. Males and females with Fontan physiology who were 12 to less than 19 years of age at enrollment.
2. Participant consent or parental/guardian consent and participant assent.
3. Participant fluent in English, Spanish, or Korean.
4. Current anti-platelet or anticoagulant therapy.

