11.1 Datasets Analyzed

No randomized subjects were excluded in the ITT and Safety populations. Approximately 97% of subjects in each treatment group were included in the Per Protocol population.

Subjects excluded from the Per Protocol population are identified in [Listing 16.2.3](#). The number and percentage of subjects in each analysis population are summarized in [Table 7](#).

Table 7: Analysis Populations

Population	Udenafil (N=200) n (%)	Placebo (N=200) n (%)	Total (N=400) n (%)
Intent-to-Treat	200 (100.0)	200 (100.0)	400 (100.0)
Safety	200 (100.0)	200 (100.0)	400 (100.0)
Per Protocol	193 (96.5)	193 (96.5)	386 (96.5)

Source: [Table 14.1.4](#)

Program: [T_14_1_4.sas](#)

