12.2.2.2 Treatment-emergent Adverse Events Related to Study Drug

Drug-related TEAEs reported by $\geq 5\%$ of subjects in the udenafil group ([Table 14.3.7A](#)) included headache (38.0%), flushing (14.5%), epistaxis (7.5%), dizziness (6.5%), nausea (6.5%), erection increased (6.3% of males), and spontaneous penile erection (6.3% of males). Drug-related TEAEs reported by $\geq 5\%$ of subjects in the placebo group included headache (22.0%), dizziness (7.0%), and flushing (6.0%). A notably greater percentage (≥ 5 percentage points) of subjects in the udenafil group as compared to the placebo group reported drug-related headache (38.0% versus 22.0%), flushing (14.5% versus 6.0%), erection increased (6.3% of males versus 0.8% of males), spontaneous penile erection (6.3% of males versus 0.8% of males), and epistaxis (7.5% versus 1.5%).

Common drug-related TEAEs (reported by $\geq 2\%$ of all subjects) are summarized in [Table 26](#). TEAEs considered not related to study drug by the Investigator are summarized in [Table 14.3.7B](#).

Table 26: Most Common (≥2% of All Subjects) Treatment-emergent Adverse Events Related to Study Drug (Safety Population)

System Organ Class Preferred Term:	Udenafil (N=200) n (%)	Placebo (N=200) n (%)
Subjects with ≥1 TEAE related to study drug	132 (66.0)	85 (42.5)
Gastrointestinal disorders	30 (15.0)	19 (9.5)
Abdominal pain upper	6 (3.0)	6 (3.0)
Nausea	13 (6.5)	7 (3.5)
General disorders and administration site conditions	19 (9.5)	15 (7.5)
Chest pain	3 (1.5)	6 (3.0)
Fatigue	5 (2.5)	7 (3.5)
Infections and infestations	14 (7.0)	7 (3.5)
Upper respiratory tract infection	7 (3.5)	3 (1.5)
Nervous system disorders	89 (44.5)	55 (27.5)
Dizziness	13 (6.5)	14 (7.0)
Headache	76 (38.0)	44 (22.0)
Migraine	5 (2.5)	4 (2.0)
Reproductive system and breast disorders	15 (7.5)	3 (1.5)
Erection increased ^a	7 (6.3)	1 (0.8)
Spontaneous penile erection ^a	7 (6.3)	1 (0.8)
Respiratory, thoracic and mediastinal disorders	27 (13.5)	13 (6.5)
Epistaxis	15 (7.5)	3 (1.5)
Nasal congestion	5 (2.5)	4 (2.0)
Vascular disorders	31 (15.5)	13 (6.5)
Flushing	29 (14.5)	12 (6.0)

TEAE=treatment-emergent adverse event

a Percentage calculated based on number of male subjects in each treatment group.

Source: [Table 14.3.7A](#)

Program: [14_3_ae_tables.sas](#)

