The primary aim of this study was to evaluate the effect of 26 weeks of treatment with udenafil on exercise capacity in adolescents with Fontan physiology. The protocol-specified primary exercise outcome was change in maximal VO_2 and secondary exercise outcomes included change in VO_2 at VAT, change in ventilatory efficiency at VAT, and work rate at VAT. All exercise measures demonstrated a favorable outcome for udenafil relative to placebo.

For maximal VO_2 , the udenafil group had a mean increase from baseline to Week 26 compared to a mean decrease in the placebo group (44.40 mL/min versus -3.65 mL/min; $p=0.071$). When standardized by each subject's body weight, the least squares mean treatment group difference was 0.64 mL/kg/min ($p=0.092$).

The following secondary efficacy endpoints measured at VAT also indicated greater exercise capacity in the udenafil group than the placebo group at Week 26:

- VO_2 at VAT: Mean increase (improvement) for udenafil as compared to a mean decrease in the placebo group (29.65 mL/min versus -8.01 mL/min; $p=0.023$). When standardized by each subject's body weight, the least squares mean treatment group difference was 0.78 mL/kg/min ($p=0.012$).
- VE/VCO_2 at VAT: Greater mean decrease (improvement) for udenafil as compared to placebo (-0.76 versus -0.05; $p=0.011$).
- Work rate at VAT: Greater mean increase (improvement) for udenafil as compared to placebo (3.46 watts versus 0.31 watts; $p=0.029$).

An additional efficacy aim evaluated the effect of 26 weeks of treatment with udenafil on the performance of a single ventricle. The primary measure of ventricular performance was change in MPI, which indicated improvement with udenafil versus placebo (-0.02 versus 0.01; $p=0.024$).

Common TEAEs with a notably greater incidence (≥ 5 percentage points) in the udenafil group as compared to the placebo group included headache, flushing, epistaxis, nausea, and erection increased (in males). These events have been reported with other PDE-5 inhibitors (Pfizer 2017).

There were no clinically important differences in the TEAE profile among subgroups defined by gender (female, male), race (Caucasian/White, non-Caucasian/White), ethnicity (Hispanic

or Latino/Latina, not Hispanic or Latino/Latina), age (tertiles at baseline), and weight (tertiles at baseline).

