An adverse event cluster including occurrences of hypotension (e.g., blood pressure decreased, blood pressure diastolic decreased, blood pressure systolic decreased, hypotension, procedural hypotension), loss of consciousness, dizziness (e.g., dizziness, dizziness exertional, procedural dizziness), presyncope, or syncope (syncope, syncope vasovagal) will be summarized as follows:

- The number and percent of subjects reporting at least 1 TEAE from the above cluster will be summarized by treatment group.
- The number and percent of patients reporting each of the preferred terms will also be summarized by treatment group.
- The 2 summaries will also be repeated by
 - age tertiles
 - weight tertiles.

An adverse event cluster including death, hospitalization for heart failure, and transplant will be summarized as follows:

- The number and percent of subjects reporting at least 1 TEAE from the above cluster will be summarized by treatment group.
- The number and percent of patients reporting each of the preferred terms will also be summarized by treatment group.
- The 2 summaries will also be repeated by
 - age tertiles
 - weight tertiles.

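### Epistaxis was 20 v 6 with antithrombotic therapy nearly universal, but no planned or listed table pools bleeding events per subject by arm beside the safety conclusion

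*Protocol*

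**What the plan says.** SAP 6.5.2 pools related preferred terms into two groups. One begins "An adverse event cluster including occurrences of hypotension" and goes on to loss of consciousness, dizziness, presyncope and syncope. The other is "An adverse event cluster including death, hospitalization for heart failure, and transplant will be summarized as follows". Neither covers bleeding. SAP 6.5 makes all safety summaries descriptive.

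Antithrombotic treatment is part of the setting. Inclusion criterion 4 (Protocol 9.3.1) reads "Current anti-platelet or anticoagulant therapy". Section 9.8.1 dates that criterion to protocol version 4, 31 August 2017; the SAP was final on 23 June 2016 (9.8.2.1). Section 9.3.3.1 says study drug was interrupted when such therapy had to be stopped. Table 11 gives antithrombotic use of 194 (97.0%) v 197 (98.5%).

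The text of 12.2.2 includes "flushing (14.5% versus 6.0%), epistaxis (10.0% versus 3.0%), nausea (9.5% versus 4.5" among the notable excesses, udenafil versus placebo. The Table 25 row is "Epistaxis 20 (10.0) 6 (3.0". For drug-related events, 12.2.2.2 ends its list of notable excesses with "and epistaxis (7.5% versus 1.5". Sections 12.6 and 13 repeat epistaxis among the excesses, and Tables 27 to 31 give it by arm within sex, race, ethnicity, age and weight groups. Section 13 adds "These events have been reported with other PDE-5 inhibitors". Both sections conclude that udenafil was safe and well tolerated.

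**The concern.** Bleeding terms are spread over system organ classes; epistaxis sits under respiratory disorders. Without a pooled count, a reader cannot tell how many subjects in each arm bled at all.

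That matters here because the drug was given on top of antithrombotic therapy by design, and one bleeding term shows a clear excess. The pooled cluster of special interest (12.3.1.3.2) shows no difference, at 9.0% v 9.5%, while the terms related to the observed excess are left unpooled. Section 11.4.5 also states that drug-drug interactions were not assessed. A safety conclusion for this population would be better supported with the bleeding total beside it.

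**Working it through.** **Inputs.** Safety population, Table 7: "Safety 200 (100.0) 200 (100.0) 400 (100.0", so 200 per arm. Event counts are from Tables 25 and 26, and antithrombotic use from Table 11.

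**Reported figures.** 20/200 = 10.0% and 6/200 = 3.0%; 15/200 = 7.5% and 3/200 = 1.5%. All reproduce. Antithrombotic use overall is (194 + 197)/400 = 97.75%.

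**Epistaxis, all.**
- Risk ratio: 0.10/0.03 = 3.33. SE of the log ratio = √(1/20 − 1/200 + 1/6 − 1/200) = 0.455. Interval = exp(1.204 ± 1.96 × 0.455) = 1.37 to 8.13.
- Difference: 7.0 points. SE = √(0.10×0.90/200 + 0.03×0.97/200) = 0.0244. Interval = 7.0 ± 4.8 = 2.2 to 11.8 points.
- 1/0.07 = 14.3, so about one extra subject with epistaxis per 14 treated.

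**Epistaxis, drug-related.** 15/3 gives a ratio of 5.00 (1.47 to 17.0) and a difference of 6.0 points (2.0 to 10.0).

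**Rank in Table 25, by risk ratio.** Epistaxis 3.33, vomiting 15/6 = 2.50, flushing 29/12 = 2.42, nausea 19/9 = 2.11, nasopharyngitis 20/13 = 1.54, headache 78/51 = 1.53, dizziness 0.94, upper respiratory tract infection 0.82, chest pain 0.56. On the difference scale, headache (13.5 points) and flushing (8.5) are larger.

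**Search for a pooled bleeding summary.**

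| Place | Bleeding pooled? |
|---|---|
| SAP 6.5.2, two clusters | No |
| Report 9.8.2.1 to 9.8.2.4, changes | No |
| List of safety tables, 14.3 | Pooled tables only for selected terms (14.3.15 to 14.3.17) and for death, hospitalization or transplant (14.3.18 to 14.3.20) |

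**Why term counts cannot replace it.** SAP 6.5.2 counts a subject once per preferred term. A subject with two bleeding terms enters two rows, so the number who bled lies somewhere between the largest row and the sum of the rows.

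**What the pooled result might be.** Arm counts for other bleeding terms are not in the text available. As an assumption only, add the same number of further subjects to each arm:

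| Added per arm | Counts | Risk ratio (95% CI) |
|---|---|---|
| 0 | 20 v 6 | 3.33 (1.37 to 8.13) |
| 5 | 25 v 11 | 2.27 (1.15 to 4.49) |
| 10 | 30 v 16 | 1.88 (1.06 to 3.33) |
| 20 | 40 v 26 | 1.54 (0.98 to 2.42) |

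The difference stays at 7.0 points by construction, with an interval of −0.2 to 14.2 in the last row. Unequal additions could move it either way.

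**Severity bounds from the visible text.**
- Section 12.6: dizziness was the only severe TEAE in more than one subject, so at most one severe epistaxis case.
- Section 12.3.1.2: serious TEAEs in two or more subjects were chest pain, influenza, syncope and dyspnoea, so at most one serious epistaxis case.
- Section 12.3.3: only headache led to interruption or discontinuation in more than two subjects in either arm, so at most two per arm for epistaxis.

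**The case against.** The best defence is that the report followed its SAP and hid nothing. Epistaxis is itself a bleeding event, reported by arm overall, as drug-related and by subgroup, and named as a notable excess in the same section as the safety conclusion. Every preferred term is in Table 14.3.5, with intensity, relationship and seriousness in companion tables and each event in Listing 16.2.7.1. No deaths or life-threatening events occurred. The SAP also came before the antithrombotic criterion. All of this stands; what it does not supply is a count of subjects with any bleeding.

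The timing argument is weaker than it looks. The blind was broken on 19 July 2019 (9.8.2.2), nearly 23 months after the criterion was added, and an afterload-agent subgroup was added between SAP and unblinding.

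Four stronger readings are tempting and should be resisted.
- *Epistaxis had the largest relative increase of any common event.* True only within Table 25. Erection increased in males was 7/111 v 1/128, a ratio of about 8 (1.01 to 64.6), and section 13 counts it as common. Influenza, streptococcal pharyngitis and rash cannot be ranked, because their placebo counts are not shown.
- *There is no bleeding rate by arm, or only terms above the common-event cut are tabulated.* The tables just cited contradict both.
- *Serious bleeding was increased.* Nothing visible supports this. Parts of the detail on intensity, serious events and discontinuations are not in the text available, so other bleeding terms there cannot be judged.
- *The report blames the drug class.* Section 13 says only that such events have been reported with other drugs of the class.

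**Conclusion.** The point holds as a gap in the safety summary. It is neither a departure from the SAP nor a numerical error. The epistaxis excess is 7.0 points (2.2 to 11.8), ratio 3.33 (1.37 to 8.13), with about 98% of subjects on antithrombotic agents. No pooled bleeding rate by arm stands behind the safety conclusion. The size of any total bleeding excess is unknown, and the pooled ratio may well be below 3.33. The intervals are descriptive: no safety testing was planned, and epistaxis was picked out after the results were seen. The finding that no pooled table exists rests on the SAP, the listed changes and the list of safety tables.

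**What to change.** Add one table to the report and declare it under 9.8.2.3 as a post hoc analysis added after unblinding. Leave SAP 6.5.2 as it is: writing in a cluster now would make a result-driven choice look planned.

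The table should give subjects with any bleeding TEAE by arm, counted once each, with risk difference and 95% CI, highest grade and seriousness. Fix the list of haemorrhage preferred terms, epistaxis included, in writing before counts by arm are run, and print it with the table. Any split by antithrombotic type is descriptive only; warfarin users number 14 v 8, too few to inform.

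In 12.6 and 13, state the epistaxis excess with its interval, the pooled bleeding result, and the severe and serious epistaxis counts (at most one of each on the visible text) beside the safety conclusion.

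Cost: one table from data already coded. It is post hoc, the pooled ratio may be smaller than that for epistaxis alone, and the safety statement may become less favourable.

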Table 10: Prior Medications Used by $\geq 5\%$ of Subjects in Either Treatment Group (Safety Population)

ATC Class (Level 3) ^a Preferred Drug Name	Udenafil (N=200) n (%)	Placebo (N=200) n (%)
≥ 1 non-study medication	195 (97.5)	198 (99.0)
ACE inhibitors, plain	107 (53.5)	107 (53.5)
Enalapril	55 (27.5)	62 (31.0)
Lisinopril	48 (24.0)	41 (20.5)
Antithrombotic agents	189 (94.5)	193 (96.5)
Acetylsalicylic acid	179 (89.5)	187 (93.5)
Warfarin	14 (7.0)	7 (3.5)
Beta blocking agents	16 (8.0)	18 (9.0)
Carvedilol	4 (2.0)	11 (5.5)
Beta-lactam antibacterials, penicillins	12 (6.0)	13 (6.5)
Amoxicillin	9 (4.5)	10 (5.0)
Cardiac glycosides	17 (8.5)	11 (5.5)
Digoxin	17 (8.5)	11 (5.5)
High-ceiling diuretics	18 (9.0)	14 (7.0)
Furosemide	18 (9.0)	13 (6.5)
Hypnotics and sedatives	10 (5.0)	5 (2.5)
Melatonin	10 (5.0)	5 (2.5)
Multivitamins, combinations	24 (12.0)	26 (13.0)
Multivitamins	21 (10.5)	24 (12.0)
Potassium-sparing agents	12 (6.0)	14 (7.0)
Spironolactone	12 (6.0)	14 (7.0)
Vitamin A and D, incl. combinations of the two	14 (7.0)	13 (6.5)
Colecalciferol	13 (6.5)	12 (6.0)

ACE=angiotensin-converting enzyme; ATC=Anatomical-Therapeutic-Chemical; incl=including

a Subjects prescribed 2 or more drugs within an ATC class are counted only once at the class level. Therefore, the sum of preferred drug name frequencies can exceed the class frequency.

Source: [Table 14.3.25](#)

Program: [T_14_3_25.sas](#)

All but 1 subject in each treatment group reported at least 1 concomitant medication.

Frequently reported concomitant medications ($\geq 20\%$ of subjects in either treatment group) included acetylsalicylic acid (92.5% udenafil, 96.0% placebo), enalapril (28.5% udenafil,

31.0% placebo), lisinopril (25.0% udenafil, 20.0% placebo), and paracetamol (20.5% udenafil, 14.0% placebo).

The use of concomitant medications was similar between treatment groups ([Table 11](#)). Concomitant medications are provided by subject in [Listing 16.2.8.4.1](#) and [Listing 16.2.8.4.2](#).

Table 11: Concomitant Medications Used by ≥5% of Subjects in Either Treatment Group (Safety Population)

ATC Class (Level 3) ^a Preferred Drug Name	Udenafil (N=200) n (%)	Placebo (N=200) n (%)
≥1 non-study medication	199 (99.5)	199 (99.5)
ACE inhibitors, plain	110 (55.0)	106 (53.0)
Enalapril	57 (28.5)	62 (31.0)
Lisinopril	50 (25.0)	40 (20.0)
Adrenergics for systemic use	16 (8.0)	12 (6.0)
Salbutamol	11 (5.5)	8 (4.0)
Angiotensin II antagonists, plain	11 (5.5)	5 (2.5)
Losartan	10 (5.0)	5 (2.5)

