6.5.2 Adverse Events

The number and proportion of subjects who report treatment-emergent adverse events (TEAEs) will be summarized for each treatment group. A TEAE is an event that begins after receipt of randomized study drug. All adverse events will be classified by MedDRA with respect to system organ class and preferred term.

The adverse event profile will be characterized with intensity and relationship to study drug (related, unrelated, unknown). Related adverse events will be defined as events considered possibly or probably related to treatment by the investigator. Events with unknown severity or relationship will be counted as unknown. The incidence of serious adverse events will be summarized similarly.

Subjects who report the same preferred term on multiple occasions will be counted once for the preferred term: under the highest severity when summarized by severity and under the closest relationship to study drug when summarized by relationship. If a subject reports multiple preferred terms for a system organ class, the subject will be counted only once for that system organ class.

Proportions for adverse events that are gender-specific (e.g., dysmenorrhea) will be based on the number of subjects from that gender.

The number and percentage of subjects who experience TEAEs will be summarized by treatment group for the following:

- By system organ class and preferred term
- By intensity (mild, moderate, or severe/life threatening/death), system organ class, and preferred term
- By relationship to study drug (not related or related), system organ class, and preferred term
- By weight tertile, system organ class, and preferred term
- By age tertile, system organ class, and preferred term
- Serious adverse events (SAEs) by system organ class and preferred term
- SAEs by relationship to study drug (not related or related), system organ class, and preferred term
- SAEs by weight tertile, system organ class, and preferred term
- SAEs by age tertile, system organ class, and preferred term

CONFIDENTIAL

- Adverse events resulting in discontinuation of study drug by system organ class and preferred term

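### Table 25 and the subgroup TEAE tables select terms on incidence pooled over both arms, so 5 of the 14 TEAEs at 5% or more on udenafil are missing from them, and the gender, race and ethnicity conclusion rests on the reduced set.

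*Protocol*

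**What the plan says.** Section 12.2.2 of the study report (the Protocol document) first lists, for each arm separately, the TEAEs reported by at least 5% of that arm, citing Table 14.3.5. The udenafil list begins "headache (39.0%), flushing (14.5%), epistaxis (10.0%), nasopharyngitis (10.0%), nausea (9.5%), dizziness (8.5%), vomiting (7.5%), upper respiratory tract infection (7.0" percent) and continues "erection increased (6.3% of males), spontaneous penile erection (6.3% of males), influenza (5.5%), chest pain (5.0%), pharyngitis streptococcal (5.0%), and rash (5.0" percent). That is 14 terms. The placebo list includes fatigue at 5.5%. The same section then names the terms that differ by 5 points or more in favour of placebo, again citing Table 14.3.5. Erection increased is one of the five named.

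The table that follows uses another rule: "Table 25: Most Common (≥5% of All Subjects) Treatment-emergent Adverse Events (Safety Population"). Section 12.2.3 opens by limiting its subgroup review to terms at 5% or more of all subjects. Tables 27 to 31 (gender, race, ethnicity, age tertile, weight tertile) carry that limit in their titles, and so do Tables 14.3.4A to 14.3.4F in the section 14.3.1 list. The drug-related table has the same form with a lower cut: "Table 26: Most Common (≥2% of All Subjects) Treatment-emergent Adverse Events Related to Study Drug (Safety Population").

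The medication tables in section 11.2 select by arm: "Table 11: Concomitant Medications Used by ≥5% of Subjects in Either Treatment Group (Safety Population"), and Table 10 likewise.

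SAP 6.5.2 asks for TEAEs by system organ class and preferred term and sets no display threshold. It adds a rule for "Proportions for adverse events that are gender-specific": they are to use the number of subjects of that sex.

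Sections 12.6 and 13 conclude that the TEAE profile shows no clinically important differences across gender, race, ethnicity, age and weight subgroups.

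**The concern.** With equal arms, a pooled 5% cut keeps a term only if the two arm rates add up to 10% or more. A term that is frequent on drug and rare on placebo is therefore easier to lose than one equally frequent in both arms. For a table meant to display what the drug does, that is an unhelpful direction.

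Two things are at stake. One is whether a reader can see both arms' figures for every term that is common on udenafil. The other is whether the subgroup statement in sections 12.6 and 13 was reached with all the common terms in view. The second matters most for gender, race and ethnicity, because the section 14 tables listed for those breakdowns carry the same pooled limit.

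**Working it through.** **Inputs.** Safety population, Table 7: "Safety 200 (100.0) 200 (100.0) 400 (100.0"), that is 200, 200 and 400. Males, Table 8: 111 udenafil, 128 placebo. Arm counts: Table 25. Arm percentages for the other terms: the section 12.2.2 text.

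**Reproducing Table 25.** The cut is 0.05 × 400 = 20 subjects. Pooled counts (udenafil + placebo):

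| Term | Sum | Pooled % |
|---|---|---|
| Headache | 78 + 51 = 129 | 32.25 |
| Flushing | 29 + 12 = 41 | 10.25 |
| Dizziness | 17 + 18 = 35 | 8.75 |
| Nasopharyngitis | 20 + 13 = 33 | 8.25 |
| Upper respiratory tract infection | 14 + 17 = 31 | 7.75 |
| Nausea | 19 + 9 = 28 | 7.0 |
| Chest pain | 10 + 18 = 28 | 7.0 |
| Epistaxis | 20 + 6 = 26 | 6.5 |
| Vomiting | 15 + 6 = 21 | 5.25 |

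All nine reach 20, so the table follows its stated rule.

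**Missing terms.** There are 14 udenafil terms and 9 are shown, so 14 − 9 = 5 are missing (36%). Chest pain and rash are both 5.0% on udenafil. Chest pain stays because 18 placebo subjects had it; rash goes. The count of 14 uses male denominators for the erection terms, as the SAP requires. Over all 200 udenafil subjects each is 7/200 = 3.5%, and the count becomes 3 missing of 12.

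**Erection increased.** 7/111 = 6.3% against 1/128 = 0.8% of males, a difference of 5.5 points. Pooled it is 8/400 = 2.0%, or 8/239 = 3.3% of males. It fails the 5% cut either way.

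**What the text allows for the unprinted placebo counts.** Two constraints apply. The term is absent from Table 25, so the pooled count is at most 19. It is absent from the list of differences of 5 points or more, so the gap is below 10 subjects of 200.

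- Influenza, 11 on udenafil: at most 19 − 11 = 8 and more than 11 − 10 = 1, so 2 to 8 on placebo.
- Streptococcal pharyngitis and rash, 10 each: at most 19 − 10 = 9 and more than 0, so 1 to 9 on placebo.
- Spontaneous penile erection, 7/111 on udenafil: one placebo case would give 6.31 − 0.78 = 5.53 points and a place on the list, so at least 2 (6.31 − 1.56 = 4.74 after rounding). It is not in the placebo list at 5% or more, so at most 6 (6/128 = 4.7%). Table 26 prints only the drug-related placebo count, 1.

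**Direction of the rule.** Assume a true udenafil rate of 7% and independent binomial counts in 200 per arm. The probability that the two counts sum to less than 20 is:

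| Assumed placebo rate | Probability dropped |
|---|---|
| 1% | 0.82 |
| 3% | 0.47 |
| 5% | 0.17 |
| 7% | 0.04 |

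In counts, 19 against 0 is 4.75% pooled and left out; 10 against 10 is 5.0% and shown.

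**Under the either-arm rule.** 9 shown + 5 udenafil terms + fatigue = 15 terms.

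**The case against.** A reader might infer that terms with a large drug-to-placebo ratio were removed before the overall comparison in sections 12.6 and 13. The documents do not support that. The arm lists and the list of differences of 5 points or more are cited to Table 14.3.5, whose title carries no incidence limit. Erection increased is not in Table 25, yet it is named in 12.2.2, 12.6 and 13. The 19-against-0 case above would appear in the text for the same reason. The placebo bounds themselves assume that this list covers terms outside Table 25.

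A reader might also infer that no subgroup table shows the dropped terms. That goes too far. The age and weight tertile tables, 14.3.9A to C and 14.3.8A to C, have no cut in their titles, and section 12.2.3 quotes the erection terms from them. Table 26 prints both arms for both erection terms with male denominators, and neither term calls for a comparison between the sexes.

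Further points on the other side are fair. The cut is stated openly in each title. It is symmetric in the arms and also drops fatigue, which was common on placebo. The SAP sets no threshold, so there is no departure from it, and section 9.8.2.1 records the gender, race and ethnicity breakdowns as additions to the SAP.

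All of this stands, and it limits the consequence. It does not supply the missing placebo figures. It also does not give the gender, race and ethnicity statement a listed table that covers the dropped terms.

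**Conclusion.** The pooled rule is confirmed, and so is its effect: five of 14 common udenafil terms, plus fatigue on placebo, are absent from Table 25 and Tables 27 to 31 and, by title, would be absent from Tables 14.3.4A to F. Two consequences remain. The supplied text gives no placebo figure for influenza, streptococcal pharyngitis or rash, and no all-cause placebo rate for spontaneous penile erection. The statement of no clinically important TEAE differences by gender, race and ethnicity rests on tables that leave these terms out.

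A reader might go further and suspect a hidden signal. At the extremes of the ranges above, rash at 10 against 1 gives Fisher p = 0.011 and at 10 against 9 gives p = 1.0; influenza runs from p = 0.020 (11 against 2) to p = 0.64 (11 against 8). These counts are assumed, the ranges include almost no difference, and the plan makes no formal safety tests. They show how much the body leaves open, and nothing about what the data contain.

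The conclusion assumes that the arm lists in 12.2.2 are complete and that the section 14 titles describe their content. Section 12.2.2.1 and parts of 12.3 were not available in the copy reviewed, so a placebo figure printed there cannot be excluded. The change should be made, but nothing indicates that the overall safety conclusion would move.

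**What to change.** Select terms for Tables 25, 27 to 31 and 14.3.4A to F by incidence of 5% or more in either treatment group of the Safety population, as Tables 10 and 11 already do, using the male or female denominator for sex-specific terms. Print both arms' counts for every selected term. Table 25 goes from 9 to 15 rows by adding erection increased, spontaneous penile erection, influenza, streptococcal pharyngitis, rash and fatigue. Then reread section 12.2.3 and the subgroup sentences in 12.6 and 13 against the fuller tables, and revise them if the added terms warrant it.

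The cost is a changed filter in existing table programs and longer tables, up to six more rows in each subgroup table. No new data are needed.

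For Table 26 the same rule is optional. It would lower the entry point from 8 subjects pooled (2% of 400) to 4 in either arm (2% of 200) for terms that apply to both sexes, and would add a number of rows that cannot be known from the documents.
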